7.3 EXCLUSION CRITERIA

The exclusion criteria are:

- 1. Developmental delays
- 2. Any chronic condition, such as diabetes or asthma, that requires medication
- 3. Prematurity, or born prior to 37 weeks gestation/of pregnancy
- 4. Congenital anomalies
- 5. Failure to thrive
- 6. Allergy to strawberry
- 7. Active diarrhea (diarrhea is defined in this study as three or more loose stools per day, for two consecutive days)
- 8. Any other medicines used except anti-pyretic medicines (*pro re nata* concomitant medications are allowed)
- 9. Parental belief of lactose intolerance
- 10. History of heart disease, including valvulopathies or cardiac surgery, any implantable device or prosthetic
- 11. History of gastrointestinal surgery or disease
- 12. Milk-protein allergy
- 13. Allergy to any component of the product or the yogurt vehicle
- 14. Allergy or a hypersensitivity to the antibiotic prescribed by her/his provider
- 15. Allergy to any of the following medications:
 - a) Tetracycline
 - b) Erythromycin
 - c) Trimethoprim
 - d) Ciprofloxacin
- 16. Blood oxygen saturation <90% (if enrollment/baseline visit is completed in person and if the participant was prescribed antibiotics during a telemedicine visit)

Participants will also be asked to refrain from any probiotic foods or supplements during the entire 2 weeks of study and will be supplied with a list of these products.

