4.1.5 Safety of Use of BB-12

Lactic acid bacteria (LAB) in foods have a long history of safe use. LAB and related organisms (with the exception of enterococci) are seldom associated with infections, except in immunodeficient individuals or individuals with severe underlying illness.[40] Although bifidobacteria are not naturally found in food, they have been used as ingredients of dietary supplements and added to foods as functional ingredients for decades.[16] The BB-12 strain has been used in numerous controlled human studies in pediatric and adult populations with no adverse incidents reported. BB-12, in combination with a strain of *S. thermophilus*, was the subject of a GRAS petition to the FDA March 2002 (Agency GRAS Notice GRN 000049), where the FDA did not object to use of these bacteria in infant formula.

Although transferable antibiotic resistances are not very common among LAB, they do occur. BB-12 was evaluated for such resistance genes and was found to contain the tetracycline resistance gene *tet*(W). Nestlé provided these data to the FDA in support of its view that the presence of *tet*(W) does not affect the safety of BB-12 as an ingredient in infant formula. In

November 2005, the FDA responded to this additional information stating that:

"Based on the information provided by Nestlé, as well as other information available to FDA, the agency has no questions at this time regarding Nestlé's conclusions that the presence of the tet(W) gene in their B. lactis strain does not affect the safety of the intended use of B. lactis as an ingredient in infant formula and that the discovery of the tet(W) gene in B. lactis does not change their previous conclusion that B. lactis is GRAS for its intended use as an ingredient in infant formula."

Summary of BB-12 Safety Articles, with the identical strain we will be using:

A) Langhendries, J.P., et al., Effect of a fermented infant formula containing viable bifidobacteria on the fecal flora composition and pH of healthy full-term infants. J Pediatr Gastroenterol Nutr, 1995. **21**(2): p. 177-81.

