8.1.2 Formulation, Packaging, and Labeling

The probiotic-supplemented yogurt is composed of the investigational agent, *Bifidobacterium animalis* subsp. *lactis* (*B. lactis*) strain BB-12 (BB-12), and also contains the yogurt starter culture, YF-L702 (a mixed culture of *Streptococcus thermophilus* and *Lactobacillus delbrueckii* subsp. *bulgaricus*).

The Chr. Hansen Culture Collection (CHHC) numbers of the exact strains used in the manufacture of the yogurt blend YF-L702 are *Streptococcus thermophilus* ST5389, *Streptococcus thermophilus* ST5086, *Streptococcus thermophilus* ST4460, *Lactobacillus delbrueckii* subsp. *bulgaricus* LB4351, and *Lactobacillus delbrueckii* subsp. *bulgaricus* LB2164.

Once manufactured, the probiotic-supplemented yogurt-drink will be packaged in quart-size plastic containers, which will yield 8 servings of the 4-ounce daily dosage. Two of these containers of yogurt drink will be provided to the participants at enrollment along with the plastic cups and markings that denote levels of 2, 4, 6, and 8 ounces. The daily dose is one serving of 4-ounces of yogurt each day. This will deliver no less than 10¹⁰ CFU per day of BB-12.

Each plastic container will bear the label "Caution: New Drug-Limited by Federal (or United States) law to investigational use" in addition to its manufactured date and time.

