10.2 STOPPING CRITERIA

Drink administration may be suspended if:

- Any study participant experiences death that the DSMB believes may be related to the drink administration.
- If statistically or clinically significant amount of hospitalizations occur that the DSMB believes may be related to drink administration.
- New information from outside studies reveals that it would be unethical to continue enrolling participants in the study.
- The IRB decides that the study should be stopped.
- Any serious adverse event for which a relationship with the study product cannot be ruled out.
- The occurrence of statistically or clinically significant, similar Grade 2/moderate adverse events in the study population that the DSMB or PI believe is related to the intervention.
- A statistically or clinically significant number of severe adverse events occur in the study population.

Individuals may be withdrawn from the study for any of the following:

- Adverse events; the PI will discuss AEs with the parent/caregiver, and possibly
 with the participant's physician, as needed, to determine whether the participant
 should be withdrawn from the study.
- If parents/caregivers or participants are deemed to be non-cooperative (e.g. refuse to collect stools, participate in follow-up calls or fail to complete diaries).
- If parent/caregiver is lost to follow-up, i.e. more than 1 week without contact with study personnel during the follow-up period.
- Serious adverse events related to drink administration, as determined by PI, parent/caregiver or participant's primary care physician.

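### Section 7.3 has no explicit immune-status exclusion, so a child with a known immunodeficiency who takes no regular medicine can be enrolled, although section 4.1.5 names that group as an exception

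*Combined protocol and SAP*

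**What the plan says.** Section 4.1.5 (Safety of Use of BB-12) opens the safety case with a general statement about lactic acid bacteria and related organisms, setting enterococci apart. They are "seldom associated with infections, except in immunodeficient individuals or individuals with severe underlying illness".

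Section 7.3 lists 16 exclusions. Those closest to immune status are:

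- Criterion 2: "Any chronic condition, such as diabetes or asthma, that requires medication".
- Criterion 8: "Any other medicines used except anti-pyretic medicines", with as-needed medicines allowed.
- Criterion 4: "Congenital anomalies", without definition.
- Criterion 10: "History of heart disease, including valvulopathies or cardiac surgery, any implantable device or prosthetic".

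The 7 inclusion items in 7.2 cover age, language, refrigerator, telephone, timing of enrollment, outpatient status and antibiotic class. None concerns immune status. The title and population in the Protocol Summary speak of healthy children, and section 12.4 speaks of good general health, still subject to the inclusion and exclusion criteria.

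On exposure, section 8.1.2 says of the daily serving: "This will deliver no less than 10¹⁰ CFU per day of BB-12".

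**The concern.** The background section names two groups as exceptions to a good safety record. The eligibility list does not name the first of them, immunodeficient individuals, although criterion 10 shows that it does name specific risk groups elsewhere.

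The omission matters more because the plan depends on this list. Section 10 gives strict enforcement of the exclusion criteria as the means of preventing adverse events, and it directs attention to allergy. Section 4.3.1 lists allergy and digestive complaints as risks and does not list infection by a cultured organism. No written safeguard elsewhere replaces the missing criterion. Section 9.2 also allows enrollment to be completed virtually, which makes an explicit screening question more useful.

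What is at stake is first the safety of an individual child. For the trial, section 10.2 allows drink administration to be suspended after "Any serious adverse event for which a relationship with the study product cannot be ruled out".

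**Working it through.** This is mainly a comparison of texts. The only document figure involved is the dose, so that is reproduced first.

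**Dose.** Inputs: mean log counts per ml from Table 6 (section 8.1.7), and the 4-ounce serving from 8.1.2, taken as 118.3 ml. Formula: CFU per serving = volume in ml × 10^(mean log CFU/ml).

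- Day 0: 118.3 × 10^8.86 = 8.57 × 10¹⁰.
- Week 3: 118.3 × 10^8.48 = 3.57 × 10¹⁰.
- Week 4: 118.3 × 10^8.49 = 3.66 × 10¹⁰.
- For the 100 ml serving mentioned in 8.1.7: 7.24 × 10¹⁰ at day 0 and 3.02 × 10¹⁰ at week 3.

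At the mean counts, the stated floor of 10¹⁰ a day is met throughout shelf life. The active product is a live culture at what section 5.1.1 calls a high dose. Control children also receive lactic acid bacteria: section 8.1.3 describes fermentation with the starter culture and no heat treatment of the yogurt afterwards.

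**Eligibility.** Different children, read against 7.2 and 7.3:

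| Child | Criterion that applies | Result under the list |
|---|---|---|
| On regular immunosuppressive medicine | 8; also 2 if the condition is chronic | Excluded |
| Immune disorder under regular treatment | 8; also 2 if chronic | Excluded |
| Inborn immune defect, no regular medicine | Possibly 4, but the term is undefined and does not mention immunity | Unclear |
| Immune defect plus implanted device, gastrointestinal disease or failure to thrive | 10, 11 or 5 | Excluded |
| Known acquired immunodeficiency, no regular medicine, no other listed feature | None | Eligible |
| Immunosuppressive treatment recently ended, no other listed feature | None; criterion 8 states no look-back | Eligible, but 4.1.5 does not name this group |

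The gap is the fifth row, and the third row where criterion 4 is read narrowly.

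**Other possible safeguards.** The Baseline Health Status form does not act as a screen: section 9.2 has baseline data collected after eligibility has been confirmed. Section 13.1 names an Inclusion/Exclusion Form, but its contents are not in the documents, so nothing can be concluded from it in either direction.

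**Number of children.** The documents give no prevalence. If a fraction *p* of otherwise eligible children is affected, the expected number is 300 × *p*. For an assumed *p* of 0.1% to 1%, this is 300 × 0.001 = 0.3 to 300 × 0.01 = 3 children. Of these, 150 × *p* = 0.15 to 1.5 would be in the BB-12 arm. The range is illustrative only.

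**The case against.** The strongest reply is that the list already does most of the work. Criterion 8 removes any child on a regular medicine other than an anti-pyretic, and criterion 2 removes medicated chronic disease. Criteria 4, 5, 10 and 11 catch further children. Participants are outpatients alerted by their physician or the study team, and the stated population is healthy children. All of this stands and makes the gap narrow. It does not close it: a statement of intent is not a criterion that screening staff can apply, and criterion 4 does not mention immunity.

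A second reply is that section 4.1.5 also summarizes a trial in which a bifidobacterial formula was well tolerated by infants, many of them malnourished or immunocompromised. That is relevant, but it concerned 55 hospitalized infants and a formula described as containing *B. bifidum* and *S. thermophilus*. It does not settle the question for BB-12 at this dose. The trial in critically ill patients summarized in the same section, using a multi-strain synbiotic, reported septic complications in 33/45 versus 26/45 (P=0.12). That does not establish harm, and it does not reassure either.

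A reader might infer several stronger things that the documents do not support:

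- That any immunosuppressed child can be enrolled. Criteria 2 and 8 exclude those on regular treatment.
- That the protocol calls this product unsafe in immunodeficient children. Section 4.1.5 is a general background statement about a class of organisms, and it names two groups, not one.
- That recent steroid courses or neutropenia are named risks. They are not mentioned there.
- That one event would stop the trial. Section 10.2 says only that administration may be suspended, and the rule applies to an event in any child.

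**Conclusion.** The point holds in a limited form. Sections 4.1.5 and 7.3 do not match: the background names immunodeficient individuals as an exception to the safety record, and the eligibility list reaches them only through current medication or another listed feature. A child with a known immunodeficiency and neither of these can be enrolled and randomized under the criteria as written.

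The number of such children is probably small, but the documents do not allow it to be estimated; the 0.3 to 3 of 300 above rests entirely on an assumed prevalence. The conclusion assumes that criterion 8 refers to medicines in use at entry, since it states no look-back, and that 7.2 and 7.3 are the complete operative criteria. Sample size, power and the primary analysis are not affected. The case for acting is that the possible harm to a child is serious and the correction is cheap.

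**What to change.** Reconcile sections 4.1.5 and 7.3 by adding to 7.3 an exclusion for known immunodeficiency, whether or not the child is on medication, and put a matching yes/no question in eligibility screening for both in-person and virtual enrollment. Whether and how to cover recently ended immunosuppressive treatment is for the sponsor to decide, since 4.1.5 does not address it.

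The cost is one protocol line, one screening item and the usual IRB amendment. The Protocol Revision History shows that version 1.6 was itself an amendment adding an exclusion, so the route exists. The downside is a small number of extra screen failures, which the documents give no means of quantifying. No change to randomization, sample size or analysis is needed.

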7.4 RANDOMIZATION

The randomization scheme will be generated using permuted blocks of varying size. It will be impossible for research personnel involved with participants to adjust randomization or discern what drinks participants were receiving, ensuring true allocation concealment. Participants who receive the control product will receive all identical interventions (i.e. stool collection, follow-up, etc.) that the active group receives.

7.5 INFORMED CONSENT AND ASSENT

Informed consent is a process that is initiated prior to an individual's agreeing to participate in the study and continuing throughout an individual's study participation. Extensive discussion of risks and possible benefits of this therapy will be provided to the parents. Consent forms describing in detail the study interventions/products, study procedures, and risks are given to the parents and written documentation of informed consent is required prior to starting intervention/administering study product. The research team will discuss all information outlined in the informed consent document with prospective parents to ensure that they understand the nature of the research and can voluntarily decide whether or not to participate.

The assent process is similar to the informed consent process for adults. The research team will discuss the purpose of this research project, procedures involved, potential risks and benefits, how we will protect their personal information, compensation, freedom to withdraw (change their mind), participant responsibilities and permission to participate. The assent and informed consent processes will allow the child and parent to ask any questions and decide amongst themselves whether or not to participate. The language of the assent process will be adjusted to be age and maturity level appropriate. Assent must be affirmative. The parent or child may discontinue study participation at any time. The assent and documentation process will be as follows:

For children under the age of 7:

Only parental permission is required (signed Informed Consent form containing the required elements of consent) before study-related procedures are conducted. In some cases (e.g. children ages 5-6), the researcher may determine the child is capable of being included in the assent process. While assent will not be required, in these cases, a simple oral explanation of the study will be offered to the child. There will be no separate form but the process will be documented in the participant's study file.

For children ages 7-12 years old:

A more complete oral description of the research is given to the child, along with a one-page written simplified summary of the study (such as the elements on the Informed Consent Form). An Assent of the Child addendum to the Informed Consent Form must be completed, along with the signed parental Informed Consent form. The child's signature is not required but the assent process will be documented in the participant's study file. The Assent of the Child addendum will specify if the child chose to sign the form or if it was determined that the child did not have the capability to give assent.

In the situation where participants and their parents/guardians elect to or must sign electronically, the following will occur:

Research personnel will review the informed consent (IC), research authorization (HIPAA), and (where applicable) assent forms with a participant and their parent(s)/guardian(s), and the research team will obtain signatures via the Georgetown-licensed version of DocuSign (HIPAA compliant).

- Potential participants and their parents/guardians would be instructed to use personal (rather than public) electronic devices (computers, tablets, phones, etc.) in signing with DocuSign.
- Parents/guardians—and participants in the case of assent—would be asked to specify an email address at which they can access and sign IC, HIPAA, and assent using DocuSign.
- Once signed by the parent/guardian, electronic versions of IC and assent (where applicable) would be signed by the research staff member who obtained consent and returned via email to the parent/guardian.

7.6 PARTICIPANT STIPENDS

Participants and parents/caregivers of participants will receive compensation for their time. Compensation will be given to the parents/caregivers five times throughout the study. All stool tests will be paid for by the study and participant's insurance company will not be responsible for tests. As per Georgetown University IRB protocol and will be elucidated in the Informed Consent, the PI, Georgetown University, Penn State University and no parties involved in the study will be responsible for additional medical care that participants may need.

8 INVESTIGATIONAL PRODUCT

8.1 STUDY PRODUCT DESCRIPTION

8.1.1 Acquisition

The investigational agent, *Bifidobacterium animalis* subsp. *lactis* (*B. lactis*) strain BB-12 (BB-12), will be supplied by manufacturer, Chr. Hansen, in Milwaukee, WI.

Chr. Hansen, Inc. [name]

The investigational agent will be shipped directly from the manufacturer to The Pennsylvania State University where they will be added to the yogurt beverage.

The Pennsylvania State University
Department of Food Science
[name]
University Park, PA 16802

8.1.2 Formulation, Packaging, and Labeling

The probiotic-supplemented yogurt is composed of the investigational agent, *Bifidobacterium animalis* subsp. *lactis* (*B. lactis*) strain BB-12 (BB-12), and also contains the yogurt starter culture, YF-L702 (a mixed culture of *Streptococcus thermophilus* and *Lactobacillus delbrueckii* subsp. *bulgaricus*).

The Chr. Hansen Culture Collection (CHHC) numbers of the exact strains used in the manufacture of the yogurt blend YF-L702 are *Streptococcus thermophilus* ST5389, *Streptococcus thermophilus* ST5086, *Streptococcus thermophilus* ST4460, *Lactobacillus delbrueckii* subsp. *bulgaricus* LB4351, and *Lactobacillus delbrueckii* subsp. *bulgaricus* LB2164.

Once manufactured, the probiotic-supplemented yogurt-drink will be packaged in quart-size plastic containers, which will yield 8 servings of the 4-ounce daily dosage. Two of these containers of yogurt drink will be provided to the participants at enrollment along with the plastic cups and markings that denote levels of 2, 4, 6, and 8 ounces. The daily dose is one serving of 4-ounces of yogurt each day. This will deliver no less than 10¹⁰ CFU per day of BB-12.

Each plastic container will bear the label "Caution: New Drug-Limited by Federal (or United States) law to investigational use" in addition to its manufactured date and time.

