8.1.3 Yogurt Drink Manufacture

Yogurt drink manufacture is broken into two major activities, 1) preparation of the yogurt and 2) blending with other ingredients to prepare the drink. To make the yogurt, a yogurt base is formulated to contain 9.0% milk solids non-fat (MSNF), 1.3% fat and 3.0% sugar using skim milk, cream, non-fat dry milk and sugar. The wet ingredients (skim milk and cream) are mixed together and then blended with previously weighed dry ingredients (sugar and non-fat dried milk). After blending the yogurt mix is pasteurized and homogenized (2000 psi first stage, 500 psi second stage) at 83°C for 29 sec. The pasteurized, homogenized mix is pumped to fermentation tank and given an additional heat treatment of 85°C for 30 min to denature whey proteins, then cooled to 42°C prior to inoculation with 0.02% of the yogurt starter culture (YFL-

720). The inoculated mix is agitated for 15 minutes and then allowed to incubate quiescently until the pH reaches 4.6.

To prepare the yogurt drink the gel structure of the fermented yogurt is disrupted by agitation and blended with a mixture of pectin, 36 DE corn syrup solids, sugar and water. The pectin-containing mixture is prepared by heating water, sugar, 36DE corn syrup solids, and pectin to 80°C, holding for 1 hour. This mixture is then cooled to 40°C and added to the fermented white mass resulting in the unflavored yogurt drink base. To flavor the product, strawberry puree is then added to the yogurt drink. The composition of the yogurt drink is shown in Table 4 and the ingredients used in manufacture are listed in Table 5. At this point, a portion of the yogurt drink is homogenized (1500 psi first stage, 500 psi second stage) for a second time to create a drinkable consistency and packaged in plastic bottles. To prepare the yogurt drink containing BB12, an appropriate amount of (BB-12) is added to the yogurt drink, allowed to mix for 15 minutes and then homogenized and packaged as describe above. The packaged yogurt is stored at 4°C.

Table 4. Composition of Strawberry Yogurt Drink

Component	Composition in Yogurt Drink
Fat	1.0%
Milk Solids Non-Fat	6.8%
Sucrose	6.1%
Corn Syrup Solids	6.4%
Pectin	0.4%
Strawberry Puree	3.0%

Table 5. Ingredients for Strawberry Yogurt Drink

Component	Supplier	Specifications
Milk ¹	Land-O-Lakes	PMO^2
Nonfat Dry MilkSolids ³	Various approved vendors	COA ⁴
Granulated Sugar ³	Various approved vendors	COA
Corn Syrup Solids ³ (42 DE)	Various approved vendors	COA

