8.4.2 Storage After Arriving in Washington, DC Area

Once the yogurt drinks arrive at Georgetown University in Washington, DC, they will immediately be transferred to two refrigerators that are exclusively used for the study—one for Drink # 1-3 and one for Drink # 4-6. Each refrigerator is equipped with a lock and a thermometer. Study personnel will take a daily temperature reading in each refrigerator to ensure that the yogurt drinks are kept between 32°F and 45°F. Each refrigerator is equipped with a SENSAPHONE® 2.8K Weatherproof Temperature Sensor, which are connected to a SENSAPHONE® 400 Remote Monitoring and Alarm Notification System. The sensor system will trigger an alarm when the temperature falls below or rises above customizable limits (between 32°F and 45°F) or if there is a power failure, and will contact up to four study personnel phone numbers.

BB-12 and control yogurt products expire one month from the date of manufacture. The date of manufacture can be found printed on each bottle of the yogurt drink. Once a month, the study personnel will make arrangements with Georgetown University Facilities Management to dispose of the products before or on the date of expiration.

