8.4.5 Instructions to Participants Regarding Storage and Dosing

BB-12 and control yogurt products expire one month from the date of manufacture. The date of manufacture can be found printed on each bottle of yogurt drink. Since the drinks are only to be consumed during a 7-10-day period and deliveries to participants will coincide with the arrival of fresh product from Penn State, participants should always have enough unexpired product in their possession to continue the study. Parents/caregivers will also be advised to dispose of any product that has been left out of the refrigerator for longer than one hour. In such cases, they may contact study personnel for fresh yogurt drinks to be delivered.

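### Each bottle is to carry a manufacture time as well as a date; if that is the bottle's own packaging time, staff could group the six drink numbers by arm

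*Combined protocol and SAP*

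**What the plan says.** **The label.** Section 8.1.2 puts an investigational-use caution on every container "in addition to its manufactured date and time". Other sections describe the print differently. Section 8.4.2 says "The date of manufacture can be found printed on each bottle of the yogurt drink", and section 8.4.5 says "The date of manufacture can be found printed on each bottle of yogurt drink". Section 8.4.4 likewise refers only to manufacture dates. Expiry is one month from that date, and study personnel arrange "to dispose of the products before or on the date of expiration".

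**The process.** Section 8.1.3 makes one flavored drink and continues: "At this point, a portion of the yogurt drink is homogenized", then packaged. For the probiotic product, BB-12 is added to the drink, "allowed to mix for 15 minutes and then homogenized and packaged as describe above".

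**Handling.** Section 8.4.2 holds the bottles in two study refrigerators, "one for Drink # 1-3 and one for Drink # 4-6". Study personnel arrange home deliveries (8.4.3). Under 9.3.1 the follow-up caller asks the caregiver for the number on the bottles, and the same calls collect the primary data.

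**The blinding claim.** Section 7.4 says research personnel cannot alter the randomization or "discern what drinks participants were receiving, ensuring true allocation concealment".

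**The concern.** A blinded product should carry no mark that differs systematically by arm. A production date shared by both products meets that test. A clock time may not, because section 8.1.3 bottles the two products in separate runs.

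The staff who might see a difference are well placed to. They hold every drink number, and they have reason to read the print because they manage expiry. Once a drink number is linked to a group, the link can reach outcome collection without the caller ever seeing a stamp, because the caller asks for that number.

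The primary outcome (5.2.1) is three or more loose stools per day on two consecutive days. Whether a borderline stool or day counts leaves some room for judgement in how staff probe and record an episode. Section 7.4 relies on staff not knowing the arm and does not mention the stamp.

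**Working it through.** No planned figure depends on this point, so the check is mainly a comparison of sections.

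**Step 1: what is printed.** Section 8.1.2 has date and time; 8.4.2, 8.4.4 and 8.4.5 have date only. The descriptions differ, and nothing says the time is masked or made common to both products.

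**Step 2: whether a time could differ by arm.** Section 8.1.3 describes two homogenize-and-package runs. It does not name the first portion as the control, but no other step yields a drink without BB-12. Two readings of the stamp are possible:

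- *A common batch time.* Both products of a production day carry the same time, and the stamp reveals nothing.
- *The container's own packaging time.* If both products are made on the same day, their times fall in two separate runs, whichever comes first. How clearly the runs separate depends on a gap that the documents do not give.

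**Step 3: whether anyone could use it.** Staff hold all six drink numbers in two refrigerators. Comparing bottles of one production date could therefore group the numbers. Saying which group is BB-12 needs something more, such as knowing the run order.

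**Step 4: whether the time is needed.** Expiry, disposal and the advice to caregivers all work from the date. No rule in the protocol uses the time.

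**Step 5: what biased recording would do, as illustration only.** Inputs: 150 per arm and a 22% control rate (11.2), with Fisher's exact test at a two-sided 0.029 (11.3). Assume no true effect, and that a fraction f of BB-12 cases goes unrecorded, so the recorded BB-12 rate is 0.22 × (1 − f). All 151 × 151 possible results were enumerated, and those with p ≤ 0.029 and the lower rate on BB-12 were counted.

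| f (assumed) | Recorded BB-12 rate | Expected BB-12 cases lost (of 150 × 0.22 = 33) | Chance of a false benefit |
|---|---|---|---|
| 0 | 0.220 | 0 | 0.0101 |
| 10% | 0.198 | 3.3 | 0.0317 |
| 20% | 0.176 | 6.6 | 0.0851 |
| 30% | 0.154 | 9.9 | 0.1943 |

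The documents give no value for f and nothing that ties f to the stamp.

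**The case against.** The strongest reply is that a reader might infer several things the documents do not establish.

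- *That the stamp does sort bottles by arm.* This needs a bottle-level time and both products made on the same day. Neither is stated. The possessive in 8.1.2 favors a bottle-level time, but 8.1.3 uses manufacture for the whole process, including the shared base, so a batch time also fits.
- *That BB-12 bottles are always later, by at least the 15-minute mixing step.* Section 8.1.3 gives no clock order. BB-12 could be mixing while the other portion is bottled, so the gap could be near zero, or the order could be reversed.
- *That 7.4 is therefore false.* It fails only if the conditions above hold and staff also compare stamps across drink numbers. Two unlabelled groups do not by themselves say which is BB-12.
- *That the caller works from knowledge of arm and has free rein over the outcome.* The documents do not say that the same individuals deliver and call, and the caller asks for the number, not the time. Caregivers, or older children themselves, record bowel movements each day in a diary (5.2.2, Table 8), which is double-entered (13.1) and drawn on during the call (9.3.1). Nothing in the protocol has caregivers comparing bottles of other drink numbers.
- *That the table in step 5 measures the harm.* It would look the same for any route to unblinding.

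All of this stands, and it limits the point to a conditional one. It does not remove the point. The protocol leaves the time undefined and unmasked, and the diary narrows the room for judgement without closing it.

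**Conclusion.** The point holds as a possible route to unblinding that section 7.4 does not address, together with an inconsistency between 8.1.2 and the date-only text of 8.4.2, 8.4.4 and 8.4.5. It rests on two assumptions: that the printed time is the container's own packaging time, and that both products are made on the same production day. If either fails, stamps on bottles of one date do not separate the arms.

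The documents do not show that any unblinding occurs, which product is packaged first, or how large the gap is. The size of the effect is therefore unknown. The rise from 1.0% to 3.2%, 8.5% and 19.4% shows only how sensitive the primary test is to one-directional under-recording at assumed rates; it does not estimate the effect of the stamp.

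The change is still worth making, because the time serves no stated purpose and removing it costs very little.

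**What to change.** In section 8.1.2, delete 'and time'. Print only the manufacture date (or the expiry date), in the same form on BB-12 and control bottles of the same production day. Keep production times in the manufacturer's batch record. This also brings 8.1.2 into line with 8.4.2, 8.4.4 and 8.4.5.

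The cost is a label change, one edited sentence and slightly less traceability from the bottle itself. Expiry tracking and the analysis are unaffected.
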